### 8.4. MULTIPLE COMPARISONS/ MULTIPLICITY

No alpha adjustment for multiple comparisons will be introduced, because only the comparison between Ladarixin and placebo group on the primary efficacy endpoint will be considered as confirmatory.

### 8.5. ACTIVE-CONTROL STUDIES INTENDED TO SHOW NON-INFERIORITY OR EQUIVALENCE

Not applicable for this study.

### 8.6. EXAMINATION OF SUBGROUPS

Subgroup descriptive analyses will be performed on the efficacy endpoints (listed in paragraph 3.2.1) according to age class at Screening ( $\leq 25$  and  $> 25$  years), to fasting C-peptide (Pre-MMTT) ( $\leq$  median value and  $>$  median value) at Screening visit and to number (1 to 4) of positive auto-Ab at Screening/diagnosis. Statistical comparisons between the two treatment groups will be performed only if the number of patients (n) of the two treatment groups is quite balanced within each stratum and with  $n \geq 10$  per treatment group in each stratum. Such statistical comparisons will be performed using non-parametric statistical tests.

## 9. OUTPUT PRESENTATIONS

Appendix 1 shows conventions for presentation of data in outputs.

The templates provided with this SAP describe the presentations shell for this study and therefore the format and content of the summary tables, figures and listings to be provided.

The reference analysis set of each table and line listing is reported in the corresponding table and line listing.

---

Document: MEX0114\_SAP\_v4\_4 Final Methods.docx  
Author: [name]

Version Number: Final Version 4.4  
Version Date: [17SEP2019]

Template No: CS\_TP\_BS016 – Revision 4  
Effective Date: 01Apr2016

Reference: CS\_WI\_BS005

## 10. DISPOSITION, WITHDRAWALS AND PROTOCOL DEVIATIONS

The number of patients enrolled, a summary of analysis populations, a summary of reasons for exclusion from analysis populations, a summary of reasons for premature withdrawal of patients from the study, and an individual data listing of the patients who prematurely interrupted the treatment/study will be presented.

Furthermore, a summary and an individual data listing of protocol deviations and major protocol deviations will be produced.

## 11. DEMOGRAPHIC AND OTHER BASELINE CHARACTERISTICS

Summary demographic data and other baseline characteristics will be tabulated for the ITT population.

No statistical testing will be carried out for demographic or other baseline characteristics.

The following demographic and baseline characteristics will be reported for this study:

- Demographic variables:
  - Age (years)
  - Gender (Male, Female)
  - Race (White/Caucasian, Asian, Black or African American, Other)
- Pregnancy test result (Positive or Negative), if appropriate
- Disease-specific information:
  - Auto-antibodies results to confirm T1D diagnosis: quantitative (IAA (U/mL), GAD (IU/mL), IA-2 (U/mL), ZnT8 (U/mL)) and qualitative, i.e. positive or negative. Quantitative results at Screening visit can be considered as “Baseline values” if sample is taken within 3 weeks prior of randomization. In case of missing values then auto-antibodies non-missing values reported at CRF page 7 will be considered as “Baseline values”.
  - Baseline Auto-antibodies quantitative results (IAA (U/mL), GAD (IU/mL), IA-2 (U/mL), ZnT8 (U/mL)),
  - Baseline insulin (IU/kg/day) and HbA1c (%) results
- Vital Signs:
  - Height (cm)
  - Weight (Kg)
  - Systolic Blood Pressure (mmHg)
  - Diastolic Blood Pressure (mmHg)
  - Heart Rate (bpm)
- Baseline 12-Lead ECG:
  - ECG Result (Normal, Abnormal not clinically significant, Abnormal clinically significant)
  - QT corrected for HR with Fridericia’s formula (QTcF) (msec)
- Baseline Mixed Meal Tolerance Test: glucose, C-peptide and glucagon (time course 0-180 min, i.e. levels at the following timepoints: Basal 1, Basal 2, 15 min, 30 min, 60 min, 90 min, 120 min, 180 min). Cmax (Maximum Plasma Concentration) and Tmax (Time to reach Maximum Plasma Concentration) of the MMTT will be provided. Individual plots will be presented. Based on the observed trends, additional analyses might be performed. Cmax and Tmax will be calculated up to 180 minutes after mixed meal administration (time interval ranging from 15 min. to 180 min.).  
 Furthermore, the 2-hour AUC of C-peptide response calculation will be based on actual rather than scheduled timings and will be calculated using the trapezoidal rule. If the actual time is not recorded, the scheduled time will be used instead. Missing C-peptide values will be imputed with the average of the C-peptide value that precedes and follows the missing value. Missing data in C-peptide at 180 minutes (final) will be replaced by the last non-missing value, and the last available basal sample (time and value) will be used as the first sample in the computation of the AUC.

Document: MEX0114\_SAP\_v4\_4 Final Methods.docx  
 Author: [name]

Version Number:  
 Version Date:

Final Version 4.4  
 [17SEP2019]

Template No: CS\_TP\_BS016 – Revision 4  
 Effective Date: 01Apr2016

Reference: CS\_WI\_BS005

- Baseline MicroRNA-375 expression level (Copies/mL)
- T-cells response (T-cell proliferation (CD4) and rate of precursor (CD8)).
- Renal Reserve: Creatinine Clearance (CLcr) (mL/min) – calculated in the CRF. The formula that will be used to verify the calculation is reported in section 11.1.
- Time since first insulin injection (days) – calculated as specified in section 11.1.

Default frequency tabulations will be provided for categorical variables and descriptive summary statistics will be provided for continuous parameters.

## 11.1. DERIVATIONS

The following variables will be derived:

- “Basal” Mixed Meal Tolerance Test measurement = (Basal 1 measurement + Basal 2 measurement) / 2
- CLcr (mL/min):
  - MALE patients =  $[(140 - \text{age (years)}) \times \text{Weight (kg)}] / [\text{Serum Creatinine } (\mu\text{mol/L}) \times 0.815]$
  - FEMALE patients =  $[(140 - \text{age (years)}) \times \text{Weight (kg)}] / [\text{Serum Creatinine } (\mu\text{mol/L}) \times 0.815] \times 0.85$
- Time since first insulin injection (days) = Date of randomization – Date of first insulin injection +1

## 12. SIGNIFICANT MEDICAL HISTORY

Significant medical history information will be tabulated for the ITT population.

All verbatim terms will be assigned to a Preferred Term (PT) and will be classified by primary System Organ Class (SOC) according to MedDRA dictionary version 19.1 or higher.

Medical conditions which are not ongoing at Screening will be considered as previous diseases while those reported as “ongoing” in CRF will be considered as concomitant diseases.

Previous and concomitant diseases will be analyzed separately with frequency tables reporting the number of patients who exhibited at least one disease and showing diseases by primary System Organ Class and Preferred term.

## 13. MEDICATIONS

Medications will be tabulated for the ITT population and coded using WHO-DRL dictionary version 2016 or higher.

See Appendix 2 for handling of partial dates for medications, in the case where it is not possible to define a medication as prior or concomitant, the medication will be classified by the worst case; i.e. concomitant.

Prior medications are those which stopped prior to the date of informed consent.

Concomitant medications are those which:

- started prior to, on or after the date of informed consent and started no later than date of end study,
- AND ended on or after the date of informed consent or were ongoing at the end of the study.

The classification of medications into prior or concomitant medications as above was done for statistical purposes.

The following tables will be presented:

- A frequency tables of prior medications by primary therapeutic subgroup (3rd level ATC level subgroup) and generic name.
- A frequency tables of concomitant medications by primary therapeutic subgroup (3rd level ATC level subgroup) and generic name.

---

Document: MEX0114\_SAP\_v4\_4 Final Methods.docx  
Author: [name]

Version Number:  
Version Date:

Final Version 4.4  
[17SEP2019]

Template No: CS\_TP\_BS016 – Revision 4  
Effective Date: 01Apr2016

Reference: CS\_WI\_BS005

## 14. STUDY MEDICATION EXPOSURE

Exposure to study medication (total duration of exposure and during each treatment cycle) in days will be summarized with descriptive statistics for the SAF by treatment group.

The date of first study medication administration will be taken from the “Diary Card” form (Treatment Cycle No.1, Day 1).

In case of treatment discontinuation, the date of last study medication will be taken from the last available “Diary Card” form.

In case of 3-cycle treatment completion, the date of last study medication will be taken from the “Diary Card” Form taking the date of Treatment Cycle No. 3 Day 14.

### 14.1. DERIVATIONS

- Duration of exposure (days) for each treatment cycle = (date of last IMP dose intake – date of first IMP dose intake) +1
- Total duration of exposure (days) = sum of the duration of exposure of each treatment cycle.

## 15. STUDY MEDICATION COMPLIANCE

Data will be summarized by treatment group for SAF population with descriptive statistics.

Descriptive analyses will be presented separately by treatment group for the total number of capsules dispensed, returned and taken, the dose administered (by treatment cycle and overall) as well as the overall compliance to study medication and the compliance by treatment cycle.

Compliance will be calculated from the derived variable “*calculated number of capsules taken*”.

### 15.1. DERIVATIONS

- Overall study medication compliance = Calculated number of capsules taken / 168 capsules (theoretical no. of capsules to be taken over the study).
- Study medication compliance by cycle = Calculated number of capsules taken in each cycle / 56 capsules (theoretical no. of capsules to be taken in each treatment cycle).
- Overall dose of ladarixin administered (mg) = Calculated number of capsules taken \* 200 mg
- Dose of ladarixin administered by cycle (mg) = Calculated number of capsules taken in each cycle \* 200 mg

## 16. ANALYSIS OF EFFICACY AND SAFETY VARIABLES

All the efficacy analyses will be performed for the ITT set.

All the AUC analyses (2-hour and 15-120) will be based on actual rather than scheduled timings and will be calculated using the trapezoidal rule. If the actual time is not recorded, the scheduled time will be used instead.

C-peptide AUC values will be transformed to the  $\log(x+1)$  [selected by TrialNet as the appropriate transformation for MMTT C-peptide AUC].

C-peptide 2-hour AUC values will be calculated from 0-120 C-peptide values of the MMTT. C-peptide (15-120) above fasting AUC will be calculated on the changes from Basal in C-peptide values of the MMTT. Basal value is the average

Document: MEX0114\_SAP\_v4\_4 Final Methods.docx

Author: [name]

Version Number:

Final Version 4.4

Version Date:

[17SEP2019]

Template No: CS\_TP\_BS016 – Revision 4

Reference: CS\_WI\_BS005

Effective Date: 01Apr2016

Copyright © 2009, 2010, 2012, 2016 Quintiles Transnational Corp. All rights reserved.

The contents of this document are confidential and proprietary to Quintiles Transnational Corp. Unauthorized use, disclosure or reproduction is strictly prohibited.

of Basal #1 and Basal #2 C-peptide values in MMTT. The last non-missing time of Basal #1 and Basal #2 values will be used to calculate the time differences in the AUC.

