### 8.3. MISSING DATA

If the actual time for Mixed Meal Tolerance Test is not recorded, the scheduled time will be used.

Missing C-peptide values will be imputed with the average of the C-peptide value that precedes and follows the missing value. Missing data in C-peptide at 180 minutes (final) will be replaced by the last non-missing value.

The last available basal sample time will be used as the first sample time in the computation of the AUC, and the average of the basal sample values (Basal #1 and Basal #2) will be used as the first sample value in the computation of the AUC.

Other missing data will not be replaced.

The number of patients with missing data will be presented under the “*unknown*” category. Missing values will be included in the denominator count when computing percentages.

When continuous data will be summarized, only the non-missing values will be evaluated for computing summary statistics.

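### The two-hour C-peptide AUC is a total over unequal spans (105 to 155 min within tolerance), SAP 11 and SAP 8.3 give different first AUC values, and log(x+1) has no rule for an above-fasting AUC of -1 or less

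*SAP*

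**What the plan says.** **Span of the AUC.** SAP 16 sets the method: "All the AUC analyses (2-hour and 15-120) will be based on actual rather than scheduled timings and will be calculated using the trapezoidal rule". It names the samples, "C-peptide 2-hour AUC values will be calculated from 0-120 C-peptide values of the MMTT", and the start of the time axis, "The last non-missing time of Basal #1 and Basal #2 values will be used to calculate the time differences in the AUC". SAP 8.3 agrees: "The last available basal sample time will be used as the first sample time in the computation of the AUC". Protocol 14.4.2 allows the two basal samples anywhere from -20 to 0 min and the 120-min draw 15 min either side of nominal. No passage cuts or interpolates the AUC to 0 and 120 min, or divides it by elapsed time.

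**First AUC value.** SAP 8.3 takes the mean: "the average of the basal sample values (Basal #1 and Basal #2) will be used as the first sample value". SAP 7.2, 11.1 and 16 also define Basal as the mean; SAP 11.1 gives it as "Mixed Meal Tolerance Test measurement = (Basal 1 measurement + Basal 2 measurement) / 2". SAP 11, describing the baseline AUC, says instead that "the last available basal sample (time and value) will be used as the first sample in the computation of the AUC", which is the rule in Protocol 9.4. Item 9 of SAP 4.3 reports a new rule for missing C-peptide values, but none of its ten items mentions the move from last basal value to mean.

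**Above-fasting AUC.** SAP 16 builds it from signed changes from Basal. SAP 16.2.2 item 9 then models it after log(x+1). No rule covers x of -1 or less, and the SAP text does not state the AUC unit.

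**The concern.** A quantity called a two-hour AUC should cover the same length of time in every patient. Here a late 120-min draw or an early last basal sample enlarges the total, and an early 120-min draw shrinks it, with no change in beta-cell function. This is the primary variable, and percent change from baseline carries the timing error of two tests.

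The first-value conflict means that, read literally, baseline and follow-up AUCs could be built differently. The baseline AUC is both the denominator and a covariate for percent change.

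The log(x+1) gap could remove visit values in one direction only. A value becomes undefined because the C-peptide response to the meal was flat or falling, and SAP 8.3 leaves other missing data unreplaced. The patient's remaining visits would stay in the mixed model.

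**Working it through.** **1. Span and timing noise**

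Inputs from Protocol 14.4.2: basals -20 to 0 min; draws at 15±5, 30±5, 60±10, 90±10 and 120±15 min.

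- Last basal at 0: 120 - 15 = 105 min to 120 + 15 = 135 min.
- Extreme: 135 + 20 = 155 min.

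The protocol gives limits, not a distribution. Assumed: all times uniform within their windows, the last basal being the later of two uniform draws; four illustrative curves (flat, and 1.5-, 2- and 3-fold rises); 200,000 simulated tests per scenario; windows also scaled to a half and a quarter.

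| Windows used | Middle 90% of spans (min) | SD of log AUC as written |
|---|---|---|
| Full | 111-143 (mean 126.7) | 7.8%-8.4% |
| Half | 115-131 | 4.0%-4.2% |
| Quarter | 118-126 | 2.0%-2.1% |

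At full windows about 0.3% of spans exceed 150 min. Dividing the AUC by its actual span cuts the SD to 2.2% or less.

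**2. Primary power**

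The plan's 85% cannot be reproduced independently, because the documents give no SD. It can be back-solved:

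- Evaluable: 72 × 0.76 = 54.72, at 2:1 = 36.48 and 18.24.
- Difference/SD for 85% at one-sided 0.05: (1.645 + 1.036) × √(1/36.48 + 1/18.24) = 2.681 × 0.2868 = 0.769.
- If the 50% difference is taken as log(1.5) = 0.405, the SD is 0.405/0.769 = 0.527 (0.521 with the t distribution).

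If timing noise s is not already in that SD, power = Φ(2.681 × SD/√(SD² + s²) - 1.645):

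| SD | s = 0.04 | s = 0.08 |
|---|---|---|
| 0.3 | 84.4% | 82.8% |
| 0.52 | 84.8% | 84.3% |
| 0.7 | 84.9% | 84.6% |

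At SD 0.52 and s = 0.085 it is 84.2%. On log(1 + time-average AUC), with an assumed placebo mean of 0.2 to 0.8, it is 84.0%-84.1%. If the planning SD already contains the noise, power stays at 85% and removing the noise adds less than 1 point.

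**3. Percent change from baseline**

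If timing errors at the two visits are independent, the added SD is about 100 × ratio × √2 × 0.08. That gives 11.3 points when follow-up equals baseline, 7.9 at a ratio of 0.7 and 5.7 at 0.5, and half of these at half windows. Timing habits shared across a patient's visits would partly cancel.

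**4. First AUC value**

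Shift = (first interval/2) × (half the basal difference)/AUC. The longest first interval is from -20 to 20 min, i.e. 40 min. If the basals differ by 20% of their mean, and the curve is flat over the shortest span that starts at -20 (105 + 20 = 125 min), the shift is 20 × 0.10/125 = 1.6%. Smaller differences or rising curves give less.

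**5. Domain of log(x+1)**

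The 15-120 min AUC reaches -1 when the mean fall below Basal is 1/span. The in-tolerance span is 105 - 20 = 85 min to 135 - 10 = 125 min.

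| AUC scale | Mean fall at 105 min | Range over 125 to 85 min |
|---|---|---|
| Concentration × min | 0.0095 | 0.0080-0.0118 |
| Concentration × hour | 0.57 | 0.48-0.71 |
| Time average | 1.0 | 1.0 |

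Assumed example: Basal 0.42 and values 0.40, 0.38, 0.40, 0.42, 0.40 ng/mL at 15, 30, 60, 90 and 120 min. The AUC of changes is -0.45 - 0.90 - 0.30 - 0.30 = -1.95 ng/mL × min, so log(x+1) is undefined. With the protocol's equivalence of 0.6 ng/mL and 0.2 nmol/L, the same curve gives -0.65 nmol/L × min, which is defined. As a time average it is -1.95/105 = -0.019 ng/mL, also defined.

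**The case against.** The strongest reply is that nothing is undetermined in the two-hour AUC. Method, start time and samples are all stated, so two programmers would get the same number, and Protocol 9.4 prespecified both the actual-time trapezoid and the last-basal start. That stands. A reader might infer that the SAP lacks a rule, or that the choice was made late; the documents support neither. What remains is that the rule, followed exactly, yields totals over unequal times.

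A reader might also infer a biased treatment comparison. Draw times under double-blind conditions have no reason to differ by arm, so the noise is non-differential. Its size rests on assumed draw times and a back-solved SD, and runs four-fold from quarter to full windows.

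Fixing the limits at 0 and 120 min may look the natural remedy. It needs the meal time. Protocol 7 requires the times of assessments and samples, but no passage says that the clock time of the drink is recorded, and Protocol 14.4.2 allows 5 min to drink it. It would also clash with SAP 8.3 when the 120-min sample is missing: the SAP averages the neighbouring values equally, whereas interpolation at 120 min would weight 90 and 180 min by 2/3 and 1/3.

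On the first value, SAP 11 reads as leftover protocol text, since four other SAP sections use the mean. On the transformation, the unit may be fixed in the table shells or dataset specifications, which are not among the documents. How many values would be lost therefore cannot be derived, and a claim that many would be is unsupported.

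**Conclusion.** The point holds at minor severity, in three parts.

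- **Span.** The two-hour AUC is an unscaled total over 105 to 155 min within tolerance. The cost is precision, not validity: about 1 point of primary power or less at the SD the plan implies, and about 2 points if the SD is as low as 0.3, assuming draws fill the windows uniformly and the planning SD excludes this noise. The noise is larger in percent change from baseline if timing errors at the two visits are independent.
- **First value.** SAP 11 contradicts SAP 8.3 on the baseline AUC by at most about 1.6% for basals differing by up to 20%. The conflict cannot reach the primary t-test, which uses week 13 only and has no baseline term. The move from the protocol's last value to the mean is nevertheless missing from SAP 4.3.
- **Transformation.** log(x+1) is applied to a signed quantity without a rule at or below -1. On a concentration × min scale a mean fall of about 0.01 units is enough, and the values lost would be those of the poorest responders. On an hour or time-average scale it is unlikely. SAP 8.4 treats only the primary comparison as confirmatory, so this affects one non-confirmatory endpoint.

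**What to change.** 1. At every visit, baseline included, divide the actual-time AUC by its actual elapsed span, and multiply by 120 if a two-hour total is wanted. This uses only sample times already recorded. Limits fixed at 0 and 120 min by interpolation are an alternative only if the meal time is recorded; the SAP must then say which end of the drink is time 0 and replace the simple-average rule of SAP 8.3 for a missing 120-min sample.
2. Replace the last-basal-value wording in SAP 11 with the rule in SAP 8.3, and list the change from Protocol 9.4 in SAP 4.3.
3. State the AUC unit used before log(x+1) for every AUC endpoint, and analyse the above-fasting AUC untransformed.

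The cost is SAP wording and a few lines of derivation code, with no new data and no change to the sample size. The downside is a departure from the protocol's AUC derivation, which must be documented in SAP 4.3.

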## 16.1. PRIMARY EFFICACY ANALYSIS

### 16.1.1. PRIMARY EFFICACY VARIABLE

The primary variable is the 2-hour C-peptide AUC after the MMTT [Time point: week 13±1].

### 16.1.2. PRIMARY ANALYSIS OF PRIMARY EFFICACY VARIABLE

The 2-hour C-peptide AUC after the MMTT at week 13 ± 1 will be transformed as log(x+1) values; transformed AUC will be analyzed with Student t-test for unpaired data using PROC TTEST within SAS® to compare Ladarixin and placebo groups. The estimated treatment difference between Ladarixin and placebo will be also presented together with the corresponding 95% confidence interval.

## 16.2. SECONDARY EFFICACY ANALYSES

### 16.2.1. SECONDARY EFFICACY VARIABLES

The secondary efficacy variables are:

1. 2-hour AUC of C-peptide response to the MMTT [Time points: baseline, weeks 13±1, 26±2 and 52±2].
2. Percent change from baseline of 2-hour AUC of C-peptide response to the MMTT [Time points: weeks 13±1, 26±2 and 52±2].
3. Average (previous 3 days) insulin requirement (IU/kg/day) [Time points: baseline, weeks 13±1, 26±2 and 52±2].  
For the patients reporting “off insulin” response in the CRF the daily insulin requirement value will be conventionally set to zero in the statistical analysis.
4. HbA1c levels [Time points: baseline, weeks 13±1, 26±2 and 52±2].
5. Number of severe hypoglycemic events occurring from randomization [Time points: weeks 13±1, 26±2 and 52±2].  
A severe hypoglycemic event is defined as an event with one of the following symptoms: “Memory loss, confusion, uncontrollable behavior, irrational behavior, unusual difficulty in awakening, suspected seizure, seizure, loss of consciousness, or visual symptoms”, in which the patient was unable to treat him/herself and which was associated with either a blood glucose level < 54 mg/dL or prompt recovery after oral carbohydrate, i.v. glucose, or glucagon administration.
6. Basal (2 basal samples in the range between -20 to 0 min) to 180 min time course of C-peptide and glucose derived from the MMTT [Time points: baseline, weeks 13±1, 26±2 and 52±2].
7. Proportion of patients maintaining a residual β-cell function [Time points: baseline, weeks 13±1, 26±2 and 52±2].  
Maintenance of a residual β-cell function is defined as at least one MMTT C-peptide value > 0.2 nmol/L.
8. Proportion of patients with HbA1c < 7% and absence of episodes of severe hypoglycemia from the previous visit [Time points: weeks 13±1, 26±2 and 52±2].
9. C-peptide AUC (15-120 minutes) above fasting value [Time points: baseline, weeks 13±1, 26±2 and 52±2].

Document: MEX0114\_SAP\_v4\_4 Final Methods.docx  
 Author: [name]

Version Number:  
 Version Date:

Final Version 4.4  
 [17SEP2019]

Template No: CS\_TP\_BS016 – Revision 4  
 Effective Date: 01Apr2016

Reference: CS\_WI\_BS005

